#### 3.4.2.5 Gastrointestinal disorders

Diarrhea/colitis is the most commonly observed treatment emergent SAE when tremelimumab is used as monotherapy. In rare cases, colon perforation may occur that requires surgery (colectomy) or can lead to a fatal outcome if not properly managed. Guidelines on management of diarrhea and colitis in patients receiving tremelimumab are provided in [Appendix F](#).

#### 3.4.2.6 Endocrine disorders

Immune-mediated endocrinopathies include hypophysitis, adrenal insufficiency, and hyper- and hypothyroidism. Guidelines for the management of patients with immune-mediated endocrine events are provided in [Appendix F](#).

#### 3.4.2.7 Pancreatic disorders

Immune-mediated pancreatitis includes autoimmune pancreatitis, and lipase and amylase elevation. Guidelines for the management of patients with immune-mediated pancreatic disorders are provided in [Appendix F](#).

#### 3.4.2.8 Neurotoxicity

Immune-mediated nervous system events include encephalitis, peripheral motor and sensory neuropathies, Guillain-Barre, and myasthenia gravis. Guidelines for the management of patients with immune-mediated neurotoxic events are provided in [Appendix F](#).

#### 3.4.2.9 Nephritis

Consult with Nephrologist. Monitor for signs and symptoms that may be related to changes in renal function (e.g. routine urinalysis, elevated serum BUN and creatinine, decreased creatinine clearance, electrolyte imbalance, decrease in urine output, proteinuria, etc.)

Patients should be thoroughly evaluated to rule out any alternative etiology (e.g., disease progression, infections etc.)

Steroids should be considered in the absence of clear alternative etiology even for low grade events (Grade 2), in order to prevent potential progression to higher grade event. Guidelines for the management of patients with immune-mediated neurotoxic events are provided in [Appendix F](#).

#### 3.4.2.10 Autoimmunity

If a subject experience an AE that is thought to be possibly of autoimmune nature (e.g., thyroiditis, hepatitis, pancreatitis, thrombocytopenia, hypophysitis, diabetes insipidus), the investigator should send a blood sample for appropriate autoimmune antibody testing and should immediately consider endocrinology consultation. If specific auto-antibodies are present, the blood sample taken for storage at baseline can be tested for the presence of auto antibodies. Continuation of investigational product in the presence of immune-mediated events should be done by the investigator with consideration to risk-benefit analysis.

### **3.5 SPECIFIC PROCEDURES FOR TACE, RFA AND CRYOABLATION**

#### 3.5.1 Transarterial chemoembolization

Percutaneous procedure is performed under general anesthesia or conscious sedation. Access is obtained from the common femoral artery and selective catheterization of the superior

mesenteric and celiac arteries is performed to define anatomy and hepatic arterial supply. Super selective catheterization of hepatic artery branches feeding the tumors is then performed followed by infusion of a chemotherapeutic mixture.

Trans-arterial chemoembolization will be performed with drug eluding beads (DEB). In this case, 100mg of doxorubicin are loaded into 100-250 micron beads. The DEB are mixed with contrast and infused into the hepatic artery branches supplying the tumor. Patients undergoing trans-arterial chemoembolization are pre-medicated with analgesics, antibiotics and anti-emetics per clinical standards.

### 3.5.2 Radiofrequency ablation

Thermal ablation is a minimally invasive image guided procedure performed under general anesthesia or conscious sedation. Radiofrequency or microwave ablations are performed; the ablation zone includes the tumor and a safety margin of surrounding tissue. Thermal ablation therapy will be administered according to the manufacturer's instructions of the device. The probe chosen varies depending on the type of thermal ablation, size of the tumor. The ablation probe will be inserted into the lesion, under image guidance. After confirmation of appropriate positioning, the lesion will be heated typically for 10-15 minutes for RFA and 5-10 minutes for microwave, according to manufacturer's guidelines. The time of ablation will depend on thermal ablation technique (RF vs. microwave) as well as the size of the ablation zone desired. The ablation time might also vary depending on proximity of critical structures, patient-specific anatomy or issues. Depending on ablation zone size, several probes might be required with several heating times to achieve complete coverage of the desired ablation zone. Balloon catheter may be used in cases where the tumor is adjacent to a hepatic vein to avoid "heat sync" where the ablation zone is cooled by the blood inflow. This catheter is typically inserted from the neck vein and is then placed into a hepatic vein. Hydrodissection may also be used in cases where the tumor is adjacent to a critical structure such as the heart or colon. These organs can sustain damage from heating, therefore a catheter is inserted into the space separating them and the tumor and fluid (dextrose 5%) is administered during the ablation.

### 3.5.3 Cryoablation

The freeze zone of cryoablation effects depend upon the probe size and configuration as well as the nadir of the freeze cycle (dependent upon the specific cryogen). Two cryoablation systems are commercially available and FDA cleared for human use (Endocare / Healthtronics and Galil). Both use helium and argon gases to induce lethal temperatures locally.

The systems require argon and helium gases which produce low temperatures upon phase change from gas to liquid. The cryotherapy equipment will be an argon-helium gas system using 1.6mm or 2.4 mm cryoprobes (Endocare, Inc., Irvine, CA) or 0.049 inches = 18 gauge = 1.3 mm cryoprobes (Galil). The ice-ball diameters for these probes may vary according to the tissue and blood supply, but their freeze lengths should be comparable to the RFA system (10-30 mm). Ice-ball diameters refer to the outer 0°C margin, but cytotoxic temperatures (e.g., < -20 to -40 °C) are known to occur 3-5 mm behind visualized ice margins. A 10-20 minutes' freeze, followed by a 5-10 minutes' thaw, and a 10-20 minute re-freeze produces visible ice and necrosis by rapid and slow mechanisms (dehydration and vascular stasis). The specific times depend upon the temperatures and potentially the temperatures of any remote thermometry used to assess temperature at the margin of a freeze. Rapid intracellular ice formation causes irreversible cell

death. Cell membrane dysfunction occurs below -10 degrees C, leading to intracellular ice formation, disrupting organelles. During thawing, osmolar shifts cause cellular swelling and rupture. Apoptosis and vascular stasis may also play a role in cell death by freezing.

The probes are placed into the tumor(s) by ultrasound, CT or MRI guidance. Up to 8 simultaneous probes may be placed sequentially for simultaneous treatment (different from current monopolar RFA). 1 % lidocaine is applied to the subcutaneous tissues down to the organ of interest. The helium and argon gases are hooked up to the system, and the cryotherapy machine and software are relatively automatic at this point with the freeze, thaw, refreeze cycles as described above. The process is monitored with ultrasound and CT scans as clinically required for standard operating procedures described by the manufacturers.

#### 3.5.4 Determination of the amount of subtotal ablation.

At all times, the volume to be ablated should be within that regarded as acceptable per standard of care for ablations performed for curative intent. Certainly, this would be less than 4 cm max in cross-sectional imaging. For the purposes of this protocol subtotal ablation refers to the complete treatment of a solitary lesion in the setting of multifocal disease, leaving other lesions (both intrahepatic and extrahepatic) intact and untreated. The lesion subjected to ablation is to be chosen at the discretion of the interventional radiologist based on technical factors, such as ease of access, proximity to vessels etc.

3.6 STUDY CALENDAR

Procedure	Pre-study	Cycle 1				Cycle 2				Cycle 3				Cycle 4				D1 of every subsequent cycle 0	EOTP	LT FU r	
		1	8	15	22	1	8 (day 36)	15	22	1	8	15	22	1 (day 85)	8	15	22				
Day		1	8	15	22	1	8 (day 36)	15	22	1	8	15	22	1 (day 85)	8	15	22				
Tremelimumab a		X								X				X							
Durvalumab a		X				X				X				X							
RTA/TACE/ Cryoablation b							X														
Informed consent	X																				
Demographics	X																				
Medical history	X																				
Advance Directive c	X																				
Concomitant meds		X				X				X				X							
Adverse event evaluation		X				X				X				X							
Physical exam d	X	X				X				X				X							
Vital signs	X	X e				X e				X e				X e							
Height	X																				
Weight	X	X				X				X				X							
Performance Status	X	X				X				X				X							

Procedure	Pre-study	Cycle 1				Cycle 2				Cycle 3				Cycle 4				D1 of every subsequent cycle 0	EOTP	LT FU r	
		1	8	15	22	1	8 (day 36)	15	22	1	8	15	22	1 (day 85)	8	15	22				
Day		1	8	15	22	1	8 (day 36)	15	22	1	8	15	22	1 (day 85)	8	15	22				
CBC w/differential, Platelets f	X	X	X	X	X	X	X	X	X	X	X	X	X	X	X	X	X	X	X		
PT, INR, PTT, Fibrinogen f	X	X				X				X				X				X			
Thyroid Panel q, h		X				X				X				X b				X			
ANA	X													X							
Biochemical profile f, g	X	X	X	X	X	X	X	X	X	X	X	X	X	X	X	X	X	X	X		
Uric acid, amylase f	X	X				X				X				X				X			
Gamma glutamyltransferase i	X	X																X			
Serum aFP or Ca 19.9 q		X				X				X				X				X			
Hepatitis B and C f, j	X	X				X				X				X				X			
Urinalysis f	X	X				X				X				X				X			
Urine or serum pregnancy test	X																				

Procedure	Pre-study	Cycle 1				Cycle 2				Cycle 3				Cycle 4				D1 of every subsequent cycle o	EOTP	LT FU r
		1	8	15	22	1	8 (day 36)	15	22	1	8	15	22	1 (day 85)	8	15	22			
Day		1	8	15	22	1	8 (day 36)	15	22	1	8	15	22	1 (day 85)	8	15	22			
HLA Phenotyping	X																			
ECG	X																			
Confirmation of dx by NCI LP	X																			
Restaging radiologic Evaluation k	X					X				X										X
Tumor biopsy l	X						X				X			X						
Immune monitoring q		X				X	X n							X	X					X s
Pharmacokinetic studies m		X	X n	X n		X				X				X						X
Immunogenicity t		X				X				X				X						X s
AMA & Liver/kidney microsomal antibody q	X													X						
Tumor-specific αFP responses q		X				X								X						X s
CFSE		X				X								X						X s

Procedure	Pre-study	Cycle 1				Cycle 2				Cycle 3				Cycle 4				D1 of every subsequent cycle 0	EOT P	LT FU r
		1	8	15	22	1	8 (day 36)	15	22	1	8	15	22	1 (day 85)	8	15	22			
Day		1	8	15	22	1	8 (day 36)	15	22	1	8	15	22	1 (day 85)	8	15	22			
proliferation T cells q																				
MDSC functional assay q		X				X				X				X						
T cell activation/ICOS expression (PBMC) t		X	X n	X n		X				X				X						
Plasma-based assays for circulating receptors/ligands e.g. PDL1 t		X				X	X n			X	X n			X						
Rectal swab (optional)	X					X								X						
Phone call or e-mail																		X	X	

- a. Tremelimumab: flat dose of 75 mg q4wk (+/- 7 days) for 4 doses only. Durvalumab: flat dose of 1500 mg q4wk (+/- 7 days).
- b. RFA/TACE/cryoablation on day 36 +/- 96 hrs.
- c. Filling out of the Advance Directive Form will be offered but obtaining of it is not required. This should be done preferably at baseline but can be done at any time during the study as long as the capacity to do so is retained. For details see Section 12.4.

- d. Full physical examination at screening; targeted physical examination at other time points
- e. within 30 minutes before and within 30 minutes after infusion.
- f. If pre-study laboratory assessments are performed within 3 days prior to Day 1 they do not need to be repeated at Day 1. Results for safety bloods must be available and reviewed before commencing an infusion. For all labs, a ‘+/- 72 hr’ window applies, with the exception of those needed to determine proceeding with treatment. Labs may be performed outside of NIH.
- g. Biochemical profile: electrolytes, BUN, creatinine, AST, ALT, total and direct bilirubin, calcium, phosphorus, albumin, magnesium.
- h. Free T3 and free T4 will only be measured if TSH is abnormal. They should also be measured if there is clinical suspicion of an adverse event related to the endocrine system.
- i. Screening, Day 1 and during the study, but only if clinically indicated
- j. For viral hepatitis patients: For Hepatitis B: HBV viral load; Anti-HBc Antibody, Anti-HBe Antibody, HBeAg and quantitative HepB Ag, HBV specific immune response. For Hepatitis C: HCV viral load, anti-HCV Antibody titre.
- k. Restaging CT of chest, abdomen and pelvis (or MRI of liver if clinically indicated) scan every 8 weeks to evaluate TTP in target lesion. Post cycle 6 restaging will occur every 12 weeks until confirmed PD. However, depending on the study design and/or comparator arm, the timing of scans may change from every 8 weeks.
- l. All patients will receive a baseline mandatory biopsy. Optional biopsies will be requested on D36 and D85. Those receiving ablative therapy will have a biopsy on D36 during the ablative therapy procedure.
- m. Pre-infusion and within approximately 15 minutes post infusion.
- n. For local patients only.
- o. Patients will continue 1500 mg durvalumab q4w until end of study treatment as defined in section **3.8.1**.
- p. The end off-treatment visits will occur if patient is agreeable to coming back and physically able to return for the visits. These visits will occur approximately 60 and 90 days post the last dose of study drug. Patients declined to come, will be contacted by phone or e-mail to evaluate their status.
- q. ‘+/- 72 hr’ window applies.
- r. Long time follow up. All subjects will be followed for survival by phone call or e-mail every 6 months
- s. Every 12 weeks until PD
- t. Pre-infusion

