### **Design:**

- We will evaluate the combination of tremelimumab and durvalumab (with ablativ e therapies) in cohorts A1 (HCC; Barcelona clinic liver cancer staging system (BCLC) stage C; N=10), A2 (HCC; BCLC stages B/C; N=30) and B (BTC; N=30). The patients in cohort A1 and first 10 patients in cohort B will receive tremelimumab and durvalumab only (i.e. no interventional radiologic procedures).

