### 3 STUDY IMPLEMENTATION

#### 3.1 STUDY DESIGN

The proposed study is a pilot study combining tremelimumab and durvalumab treatment in patients with advanced HCC (Cohorts A1 and A2) either alone (Arm A1) or with cryoablation, TACE or RFA (Arms A2, A3, A4) and patients with advanced BTC (Cohort B) either alone (Arm A1) or with cryoablation or RFA (Arms A3, A4).

The decision on which interventional radiologic procedure to administer (i.e. RFA vs. TACE vs. cryoablation) will be made in consultation with the interventional radiologists. The reason for this is that there are technical considerations (size and location of lesion, main portal vein occlusion etc.) which would make one procedure preferable over the other.

- Transarterial chemoembolization is percutaneous procedure performed under general anesthesia or conscious sedation. (See 3.5.1 for details)
- Patients undergoing trans-arterial chemoembolization, RFA or cryoablation are pre-medicated with analgesics, antibiotics and anti-emetics per clinical standards. For details regarding each procedure please see 3.5.

Cohort	Population	Immune stimulating procedure	Dose level	Planned N
A1	Advanced HCC, BCLC Stage C	No ablative procedure	Tremelimumab 75mg flat dose q28 days for 4 doses Durvalumab 1500mg flat dose q28 days until EOS###	10 total
A2	Advanced HCC, BCLC Stage B/C	Cryoablation/ RFA/TACE*	Tremelimumab 75mg flat dose q28 days for 4 doses Durvalumab 1500mg flat dose q28 days until EOS**	30 total 10 trem+ dur + TACE 10 trem + dur + RFA 10 trem + dur + cryo
B	Intra/extra-hepatic cholangiocarcinoma	N= 1st 10 pts: No ablative procedure  RFA/ cryoablation	Tremelimumab 75mg flat dose q28 days for 4 doses Durvalumab 1500mg flat dose q28 days until EOS**	30 total 10 trem+ dur alone 10 trem + dur + RFA 10 trem + dur + cryo

\* For BCLC stage B patients TACE may be repeated as per standard of care

\*\* EOS = end of study treatment as defined in section 3.8.1.

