#### **3.2.2 Cohort A2**

The schema for Cohort A2 is shown below. For Cohort A2 (BCLC Stage B/C patients) TACE, RFA or cryoablation will be performed once only, on Day 36 (+/- 96hrs).

- Both BCLC stage B and C are eligible for cohort A2.
- Patients will receive 1500 mg durvalumab via IV infusion q4w for up to 4 doses/cycles and 75 mg tremelimumab via IV infusion q4w for up to 4 doses/cycles, and then continue 1500 mg durvalumab q4w. Tremelimumab will be administered first. Durvalumab infusion will start approximately 1 hour after the end of tremelimumab infusion. The duration will be approximately 1 hour for each infusion. A 1-hour observation period is required after the first infusion of durvalumab and tremelimumab. If no clinically significant infusion reactions are observed during or after the first cycle, subsequent infusion observation periods can be at the Investigator's discretion (suggested 30 minutes after each durvalumab and tremelimumab infusion).

[figure not shown]

Figure 3: Schema cohort A2

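### As extracted, the Study Calendar's tremelimumab row has no mark on day 1 of cycle 2, although its own footnote and sections 3.1 and 3.2 give four doses at 4-week intervals

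*Combined protocol and SAP*

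**What the plan says.** Five places outside the calendar marks describe tremelimumab dosing in the same way:

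- The section 3.1 design table, for every cohort: "Tremelimumab 75mg flat dose q28 days for 4 doses".
- Sections 3.2.1, 3.2.2 and 3.2.3, one for each cohort, in the same words: "75 mg tremelimumab via IV infusion q4w for up to 4 doses/cycles".
- Footnote a to the section 3.6 Study Calendar: "Tremelimumab: flat dose of 75 mg q4wk (+/- 7 days) for 4 doses only".

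The calendar row to which footnote a is attached, "Tremelimumab a", carries three marks, under day 1 of cycles 1, 3 and 4. The cell for cycle 2 day 1 is empty. The durvalumab row directly beneath is marked on day 1 of all four cycles.

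For the ablation arms, calendar footnote b gives "RFA/TACE/cryoablation on day 36 +/- 96 hrs", which the calendar header places at cycle 2 day 8. Not every arm has a procedure. The Précis states: "The patients in cohort A1 and first 10 patients in cohort B will receive tremelimumab and durvalumab only".

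**The concern.** A schedule of events is a natural working reference for ordering treatment, and all seven arms share this one. Taken by its marks, the row gives a first interval of 56 days where the written schedule has 28, and it drops one of the four planned doses.

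The day in question is not neutral for the trial's purpose. The study asks whether ablation adds to combined checkpoint inhibition, and ablation-arm patients have a biopsy during the day 36 procedure. If some patients had one tremelimumab dose before that point and others two, the regimen would not be uniform within an arm of 10. The day 36 biopsy and immune readouts would also mix two exposures.

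**Working it through.** This is a comparison of calendar cells with written schedules, so no sample-size formula applies.

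**1. The written schedule.** With the first dose on day 1 and a 28-day interval, dose k (k = 0 to 3) falls on day 1 + 28k, that is days 1, 29, 57 and 85. This gives the stated four doses. The total is 4 × 75 = 300 mg.

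**2. The calendar marks.** The header has a procedure column, a pre-study column, then days 1, 8, 15 and 22 of cycles 1 to 4. Matching each row to those columns:

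- Tremelimumab: C1D1, C3D1, C4D1 (days 1, 57, 85). Gaps: 57 − 1 = 56 days and 85 − 57 = 28 days. Total: 3 × 75 = 225 mg.
- Durvalumab: C1D1, C2D1, C3D1, C4D1.
- Ablation: C2D8, that is 29 + 7 = day 36, as the header labels it.

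The marks do not reproduce the stated four doses. The difference is the single cell at C2D1 (day 29): 300 − 225 = 75 mg, and 75/300 = 25% of the planned cumulative dose.

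**3. Has the row shifted?** No. The C3D1 and C4D1 tremelimumab marks line up with those of durvalumab, and C4D1 is the column headed day 85. One cell is empty and the rest of the row is in place. Alignment shows that columns did not move. It does not show that no single mark was lost.

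**4. Can the dosing window explain the gap?** No. Section 3.4 and footnote a allow 7 days either way, so an interval of 28 ± 7 = 21 to 35 days. The marked first gap is 56 days.

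**5. Position relative to the procedure.** Nominally 36 − 29 = 7 days. With day 29 ± 7 (days 22 to 36) and day 36 ± 96 hours (days 32 to 40), the separation runs from 40 − 22 = 18 days before the procedure to 36 − 32 = 4 days after it. The contrast of one dose against two before ablation is therefore nominal.

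**6. Who is concerned.** The empty cell applies to all seven arms. The pre-ablation contrast applies only to the procedure arms: 30 in cohort A2 plus 20 in cohort B, 50 planned patients.

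**7. Another row of the same calendar.** Pharmacokinetic sampling is marked at C2D1, and footnote m times it before the infusion and shortly after it. The only assay that section 5.3.1 describes measures tremelimumab. Durvalumab is also infused that day, so this is not proof. Still, a post-infusion tremelimumab sample fits a tremelimumab infusion at C2D1 better than an empty cell does.

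**8. Section 10.** The stated 82% power depends on 10 patients per arm, 15% against 50%, and a one-sided 0.10 exact test. Requiring 4 or more of 10 gives a type I error of 0.050 and power of 0.828, close to the stated figure. The dose count does not enter.

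**The case against.** The strongest objection is that the empty cell may not be in the protocol at all. The calendar was read from PDF by a program, and individual marks in it are visibly unreliable. On the same calendar block, the column for later cycles is blank even for durvalumab, although footnote o continues that drug every 4 weeks. The biopsy row shows a mark at cycle 3 day 8 that footnote l does not mention. The restaging row is marked at cycle 2 day 1, although footnote k sets 8-week intervals. A lost mark would leave exactly the pattern seen here. This stands. It is why the source page comes first, and why confidence in the point is low.

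The second objection concerns consequence. A reader might infer that the calendar lays down a three-dose schedule, or that a site using it will leave out the day 29 dose. The documents support neither reading. The row label sends the reader to footnote a, which gives the interval and the number of doses. The design table and all three cohort schedules say the same, and the sampling row fits them. Section 7.4.1 also has the research team discussing each patient weekly, which gives an opportunity to notice the conflict. This also stands: omission is possible, not established.

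Neither objection removes the inconsistency from the text as it reads. If the cell is blank on the source page, the row and its own footnote disagree about a dosing day.

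**Conclusion.** The point holds as an internal inconsistency to be checked and, if confirmed, reconciled. The extracted calendar row shows three tremelimumab marks (days 1, 57, 85), while footnote a, section 3.1 and sections 3.2.1 to 3.2.3 give four doses (days 1, 29, 57, 85).

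If staff followed the marks alone, the planned total would be 225 mg in place of 300 mg, 25% less. In the 50 planned ablation-arm patients there would nominally be one dose before the procedure in place of two. Those sizes assume nominal days, and that the reader overlooks footnote a and sections 3.1 and 3.2. They are a worst case and not an expected effect.

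The conclusion rests on the source page showing the same empty cell. If it carries a mark there, the point falls away. Endpoint definitions, power and analysis are untouched either way. A reader might also infer that the calendar must be the faulty side because more passages agree against it. The agreement is worth reporting, but the intended schedule is for the sponsor to confirm.

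**What to change.** Look at the cycle 2 day 1 cell of the tremelimumab row on the source page of the section 3.6 calendar. If it is marked there, nothing needs to change. If it is blank, the sponsor confirms the intended schedule, and the calendar row, footnote a, the section 3.1 table and sections 3.2.1 to 3.2.3 are brought into line so that all show the same dosing days. The pharmacokinetic and immunogenicity sampling marks at that visit should be checked against the result.

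The check takes minutes. Any correction is a small clerical edit for the next amendment, with no effect on sample size or analysis. If patients have already been treated, the dosing records will show which schedule was followed at cycle 2.
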